10.2 Analysis Execution

Analyses are planned when all implanted subjects have completed his/her six-month follow-up, and when all implanted subjects have completed his/her five-year follow-up. A final report will be prepared once all implanted subjects have completed his/her five-year follow-up and all data collection has ended. See section 10.3 for additional analyses.

10.3 Interim Analysis

An initial analysis is planned when the first 50 implanted subjects have completed his/her six-month follow-up; however initial analyses may be performed earlier if enrollment is slower than expected. Initial analyses will assess all safety and efficacy endpoints based on available data.

There are no formal interim analyses planned for purposes of “early-win” assessment, futility, or sample size confirmation.

10.4 Safety Endpoints

Safety endpoints include:

1. All-cause and cardiovascular mortality at 30 days and 6 months
2. All stroke (disabling and non-disabling) at 30 days and 6 months
3. Myocardial infarction (periprocedural and spontaneous) at 30 days and 6 months
4. Acute kidney injury at 30 days and 6 months
5. Major vascular complications at 30 days and 6 months
6. Life-threatening bleed at 30 days and 6 months
7. New permanent pacemaker implantation (PPI) at 30 days and 6 months
8. New intraventricular conduction delays at 30 days and 6 months
9. New-onset atrial fibrillation at 30 days and 6 months
10. Valve-related dysfunction requiring repeat procedure at 30 days and 6 months

Analysis for the safety endpoints will be based on the “Attempted Implant” data set. For each time-related event, Kaplan-Meier rates (cumulative incidence) and 95% two-sided confidence intervals at 30 days and 6 months will be calculated. Safety endpoints will be based on CEC adjudicated events.

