10.6 Additional Outcome Measures

The following outcome measures will be also be evaluated:

1. All-cause and cardiovascular mortality annually through 5 years
2. All stroke (disabling and non-disabling) annually through 5 years
3. Cardiovascular and heart failure hospitalizations at annually through 5 years
4. Heart failure events at annually through 5 years
5. New York Heart Association (NYHA) functional classification at 30 days, 6 months, and annually through 5 years
6. Change in New York Heart Association (NYHA) functional classification from baseline annually through 5 years
7. Kansas City Cardiomyopathy (KCCQ) annually through 5 years
8. Hemodynamic performance metrics by Doppler echocardiography
 - Mean aortic gradient annually through 5 years
 - Effective orifice area annually through 5 years
 - Degree of total, para, and transvalvular prosthetic regurgitation annually through 5 years
 - Incidence of moderate and severe patient-prosthesis mismatch (PPM) annually through 5 years
9. Prosthetic valve thrombosis 30 days, 6 months, and annually through 5 years
10. Prosthetic valve endocarditis at 30 days, 6 months, and annually through 5 years

11. Bioprosthetic valve dysfunction (BVD) at 30 days, 6 months, and annually through 5 years
12. Bioprosthetic valve failure (BVF) at 30 days, 6 months, and annually through 5 years
13. Valve-related dysfunction requiring repeat procedure annually through 5 years

Analyses of the additional outcome measures will be descriptive. The attempted implant set will be used for safety and quality of life outcomes. However, the outcomes involving echocardiographic variables will be analyzed for the implanted set. Continuous variables will be summarized as the number of subjects, mean, standard deviation, median, first and third quartiles, minimums, and maximums. Categorical variables will be summarized as counts and percentages. For each time-related event, Kaplan-Meier rates (cumulative incidence) and 95% two-sided confidence intervals will be calculated.

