7.2 General Methodology

Continuous variables will be summarized descriptively with number of observations, mean, standard deviations, median, first and third quartiles, minimums and maximums. Categorical data will be presented as counts and percentages.

For time-to-event outcomes using Kaplan-Meier methods, the time points of 30 days, 6 months, 1 year, 2 years, 3 years, 4 years, and 5 years will correspond to 30, 183, 365, 730, 1095, 1460, and 1825 days post-implant, respectively. For each applicable time point, the event or event-free rate, the number of subjects at risk, the number of subjects with an event, the Greenwood standard error of the estimate, and the log-log transformed 95% confidence interval using the Greenwood standard error will be reported. For subjects with an event, the date of event will be based on the first event occurrence. For subjects without an event, date of censoring will be based on the latest of all follow-up visits, assessments, and events (for non-death events).

All statistical analyses will be performed using SAS version 9.4 or higher (SAS Institute, Cary, North Carolina, USA) or other widely accepted statistical or graphical software.

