7.9 Evaluation of Objectives

7.9.1 Safety Endpoints

The following safety endpoints are defined and will be analyzed:

1. All-cause and cardiovascular mortality at 30 days and 6 months
2. All stroke (disabling and non-disabling) at 30 days and 6 months
3. Myocardial infarction (periprocedural and spontaneous) at 30 days and 6 months
4. Acute kidney injury at 30 days and 6 months
5. Major vascular complications at 30 days and 6 months
6. Life-threatening bleed at 30 days and 6 months
7. New permanent pacemaker implantation (PPI) at 30 days and 6 months
8. New intraventricular conduction delays at 30 days and 6 months
9. New-onset atrial fibrillation at 30 days and 6 months
10. Valve-related dysfunction requiring repeat procedure at 30 days and 6 months

Safety endpoints will be adjudicated by the Clinical Events Committee (CEC) and analysis will be based on data collected on the CEC adjudication form. Safety endpoints will be analyzed with Kaplan-Meier survival analysis methods according to Section 7.2. Safety endpoints will be analyzed using the Attempted Implant population.

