7.9.3 Additional Outcome Measures

The following outcome measures will be also be evaluated:

1. All-cause and cardiovascular mortality annually through 5 years
2. All stroke (disabling and non-disabling) annually through 5 years
3. Cardiovascular and heart failure hospitalizations annually through 5 years
4. Heart failure events annually through 5 years
5. New York Heart Association (NYHA) functional classification at 30 days, 6 months, and annually through 5 years
6. Change in New York Heart Association (NYHA) functional classification from baseline annually through 5 years
7. Kansas City Cardiomyopathy (KCCQ) annually through 5 years
8. Hemodynamic performance metrics by Doppler echocardiography
 - Mean aortic gradient annually through 5 years
 - Effective orifice area annually through 5 years
 - Degree of total, para, and transvalvular prosthetic regurgitation annually through 5 years
 - Incidence of moderate and severe patient-prosthesis mismatch (PPM) annually through 5 years
9. Prosthetic valve thrombosis 30 days, 6 months, and annually through 5 years
10. Prosthetic valve endocarditis at 30 days, 6 months, and annually through 5 years
11. Bioprosthetic valve dysfunction (BVD) at 30 days, 6 months, and annually through 5 years
12. Bioprosthetic valve failure (BVF) at 30 days, 6 months, and annually through 5 years
13. Valve-related dysfunction requiring repeat procedure annually through 5 years

Additional Outcomes Measures 1-10 and 13:

Analysis for additional outcome measures 1-8 and 13 will follow the analysis methods defined for the same safety and efficacy endpoints at earlier timepoints described in Section 7.9.1 and 7.9.2, respectively. Prosthetic valve thrombosis and prosthetic valve endocarditis, additional outcome measures 9 and 10, will be analyzed with Kaplan-Meier analysis as described in Section 7.2. The analysis

of additional outcome measures 9 and 10 will be based on CEC adjudications using the Attempted Implant set.

Additional Outcome Measure 11 - Bioprosthetic valve dysfunction (BVD)⁽¹⁾ at 30 days, 6 months, 1 year:

Bioprosthetic valve dysfunction (BVD) is defined as meeting any of the following:

- Moderate or severe stenosis defined as any of the following:
 - Peak aortic velocity > 4 m/s OR mean aortic gradient > 40 mmHg, AND EOA < 0.8 cm²
 - Peak aortic velocity > 4 m/s OR mean aortic gradient > 40 mmHg, AND EOA ≥ 0.8 cm², AND DVI < 0.25

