7.10 Safety Evaluation

Adverse events will be summarized by MedDRA System Organ Class (SOC) and High-level Term (HLT) at 30 days, 6 months, 1 year, and annually through 5 years. The number of events, number of subjects with event, and the Kaplan-Meier event rate (cumulative incidence) will be reported for each category and time point. Device related, procedure-related, and Serious Adverse Events (SAEs) will be reported similarly. A listing of adverse events will also be reported and will at minimum include the adverse event category, severity, treatment received, resolution, and investigator assessment of relationship to the device and procedure.

Additionally, listings of subject deaths, all device deficiencies, and device deficiencies which could have led to a serious adverse device effect will be reported.

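### The annual outcomes to 5 years report 1 minus Kaplan-Meier as cumulative incidence while censoring competing deaths, which overstates incidence slightly but systematically

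*Protocol*

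**What the plan says.** For time-related safety endpoints, protocol 10.4 states: "Kaplan-Meier rates (cumulative incidence) and 95% two-sided confidence intervals at 30 days and 6 months will be calculated". Section 10.5 names the same estimator and label for time-related efficacy endpoints. Section 10.6 does the same for the annual outcomes: "For each time-related event, Kaplan-Meier rates (cumulative incidence) and 95% two-sided confidence intervals will be calculated". That list opens with "All-cause and cardiovascular mortality annually through 5 years", so a cause-specific death rate will stand beside the all-cause rate.

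The SAP carries this through:

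- 7.9.1: "Safety endpoints will be analyzed with Kaplan-Meier survival analysis methods according to Section 7.2".
- 7.9.3: "Analysis for additional outcome measures 1-8 and 13 will follow the analysis methods defined for the same safety and efficacy endpoints at earlier timepoints". Valve thrombosis, endocarditis and bioprosthetic valve failure (BVF) are also assigned to Kaplan-Meier there.
- 7.10, for adverse events through 5 years: "the Kaplan-Meier event rate (cumulative incidence) will be reported for each category and time point".

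For subjects without the event, SAP 7.2 says the "date of censoring will be based on the latest of all follow-up visits, assessments, and events". SAP 7.4 censors dropouts at discontinuation. Neither document gives death any status other than censoring for a non-fatal event, or mentions competing risks.

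**The concern.** Someone who dies without a stroke can no longer have one. Censoring that person at death treats them as still at risk, unobserved, with the same future risk as the survivors. 1-KM then describes a hypothetical population in which nobody dies of other causes. Cumulative incidence means the share of real patients who have the event by a given time, so the label in both documents does not fit these outcomes. The same holds for cardiovascular mortality, where non-cardiovascular death competes.

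Protocol objective 2 is to estimate event rates for endpoints that pivotal studies may use. A figure labelled cumulative incidence is likely to be read as the proportion of patients expected to have the event. The exposure grows with follow-up: subjects are 65 or older, and the life-expectancy exclusion removes only those with less than 24 months because of non-cardiac disease, so some deaths over 5 years are to be expected.

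**Working it through.** **Inputs.** From the documents: the estimator, the censoring rule, the time points (30 and 183 days, then yearly to 1825 days) and 75 subjects. The documents state no mortality or event rate, so there is no plan figure to reproduce. Every rate below is an assumption.

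**Direction.** Both estimators add the same hazard increments at each event time. Kaplan-Meier weights each by the estimated chance of being event-free, ignoring death. Aalen-Johansen weights it by the chance of being event-free and alive, which cannot be larger. So 1-KM is never below the Aalen-Johansen estimate. This needs no assumption about hazards.

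**Size at 5 years.** With event hazard h, competing-death hazard d and independent constant hazards:

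- 1-KM = 1 − exp(−5h)
- true incidence = h/(h+d) × [1 − exp(−5(h+d))]
- d = −ln(1 − mortality)/5

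Fix the true incidence at 10%, solve for h, then compute 1-KM:

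| Competing mortality | d per year | h per year | 1-KM | Relative excess |
|---|---|---|---|---|
| 10% | 0.0211 | 0.0222 | 10.5% | 5.3% |
| 15% | 0.0325 | 0.0229 | 10.8% | 8.2% |
| 20% | 0.0446 | 0.0236 | 11.1% | 11.3% |
| 30% | 0.0713 | 0.0252 | 11.8% | 18.4% |

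Over a wider assumed grid (competing mortality 5% to 40%, 1-KM 5% to 30%), the 5-year excess runs from 0.12 to 6.2 percentage points.

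**Cardiovascular death.** Suppose 25% die by 5 years, half from cardiovascular causes. The true figure for each cause is 12.5%. The cause-specific hazards are equal, so 1-KM for each is 1 − √0.75 = 13.4%. The two sum to 26.8%, more than the 25% who died. With all-cause mortality of 10%, 20% or 30% split evenly, 1-KM for cardiovascular death is 5.1%, 10.6% or 16.3%, against 5%, 10% or 15%.

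**30 days and 6 months.** A true 6-month incidence of 10.0% reads 10.1% to 10.2% with 2% to 3% mortality by then. For an early event, the excess cannot exceed 1-KM times the mortality by that time: with 15% pacemaker implantation and 2% mortality at 30 days, at most 0.15 × 0.02 = 0.3 points.

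**Against sampling error.** Take 75 subjects, no censoring and a 10% rate. The standard error is √(0.9 × 0.1/75) = 0.0346. On the log-log scale it is 0.0346/(0.9 × |ln 0.9|) = 0.365. The 95% limits are 1 − 0.9^exp(∓1.96 × 0.365), or 5.0% to 19.4%. A simulation of 75 subjects (4000 runs, assumed 10% dropout, 20% competing mortality, 1-KM set at 20%) gave a mean Kaplan-Meier rate of 20.1%, a mean Aalen-Johansen rate of 18.1%, and a mean interval width of about 20 points.

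**The case against.** Much of the case for leaving the plan alone stands as a limit on the point.

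- *Time points.* All key endpoints are at 30 days and 6 months, where the bias is negligible. The annual rates are additional outcome measures.
- *Scope.* A reader might infer that every non-fatal event is affected out to 5 years. The documents do not support that. Bioprosthetic valve dysfunction (BVD) is a count and percentage (SAP 7.9.3). Myocardial infarction, acute kidney injury, major vascular complications, life-threatening bleed, pacemaker implantation, conduction delay and new atrial fibrillation have no annual outcome measure and reach 5 years only through the adverse-event tables. BVF counts valve-related death as an event, so only other deaths compete with it.
- *Pivotal sizing.* A reader might also infer that a pivotal study will be mis-sized. Objective 2 names no time point, and no section says the 5-year rates will be used for sizing. A time-to-event calculation may need the cause-specific hazard, which under independent constant hazards −ln(KM)/t recovers without bias, with deaths entered separately.
- *Size.* The mortality range is assumed. Subjects are NYHA class I with LVEF of at least 50% and several comorbidity exclusions. Protocol 13.8.1 classes sudden, unwitnessed and unknown-cause deaths as cardiovascular, which reduces competing non-cardiovascular death.
- *Transparency.* Numbers at risk, numbers with events, deaths by visit and all-cause mortality will all be reported.

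These points narrow the consequence. None makes 1-KM a cumulative incidence, and a table of deaths does not correct the rate printed beside it.

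**Conclusion.** The point holds for the Kaplan-Meier outcomes reported annually to 5 years other than all-cause mortality: cardiovascular mortality, stroke, cardiovascular and heart failure hospitalization, heart failure events, valve thrombosis, endocarditis, BVF, repeat procedure, and the adverse-event tables. The upward direction is certain wherever competing deaths precede later events. The size rests on assumed mortality and constant hazards: 0.5 to 1.8 points on a true 10% for 10% to 30% competing mortality at 5 years. That is well inside the sampling error at 75 subjects, but it is systematic, so a wide interval does not remove it. The key endpoints are not materially affected, and a mis-sized pivotal study is a possible consequence, not one the documents establish.

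**What to change.** Amend SAP 7.2, 7.9.3 and 7.10 and protocol 10.4 to 10.6:

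1. Keep Kaplan-Meier for all-cause mortality.
2. For the other outcomes now analysed by Kaplan-Meier, report the Aalen-Johansen cumulative incidence with log-log 95% limits. Name its variance estimator, because the Greenwood standard error in SAP 7.2 is specified for Kaplan-Meier.
3. Define the competing event: death in general; non-cardiovascular death for cardiovascular mortality; deaths not meeting the BVF definition for BVF.
4. Allow 1-KM as a supportive column without the cumulative incidence label.

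BVD needs no change. The cost is wording and a standard software option. No new data are needed: the Death eCRF already records date and category of death (protocol 7.2), and the Clinical Events Committee adjudicates all deaths (protocol 7.7). Affected rates will be the same or slightly lower.

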10.5 Efficacy Endpoints

Efficacy endpoints include:

1. Device success (VARC-2)
2. Cardiovascular and heart failure hospitalizations at 30 days and 6 months
3. Heart failure events at 30 days and 6 months
4. Hemodynamic performance metrics by Doppler echocardiography at discharge, 30 days, and 6 months
 - Mean aortic gradient

- Effective orifice area
 - Degree of total, para, and transvalvular prosthetic regurgitation
 - Incidence of moderate and severe patient-prosthesis mismatch (PPM)
5. Change from baseline in New York Heart Association (NYHA) functional classification at 30 days and 6 months
 6. Change in six-minute walk test (6MWT) from baseline at 6 months
 7. Change in Kansas City Cardiomyopathy (KCCQ) from baseline at 30 days and 6 months
 8. Change in left ventricular ejection fraction (LVEF) from baseline at 6 months
 9. Change in peak global longitudinal strain (GLS) from baseline at 6 months
 10. Change in left ventricular filling pressure (E:e') from baseline at 6 months
 11. Change in stroke volume index (SVI) from baseline at 6 months
 12. Change in NT-pro B-type natriuretic peptide (NT-proBNP) from baseline at 6 months

Analyses of the efficacy endpoints will be descriptive. The attempted implant set will be used for safety and quality of life outcomes. However, the efficacy endpoints involving echocardiographic variables will be analyzed for the implanted set. Continuous variables will be summarized as the number of subjects, mean, standard deviation, median, first and third quartiles, minimums, and maximums. Categorical variables will be summarized as counts and percentages. For each time-related event, Kaplan-Meier rates (cumulative incidence) and 95% two-sided confidence intervals will be calculated. Efficacy endpoints involving echocardiographic variables will be based on ECL reported data.

10.6 Additional Outcome Measures

The following outcome measures will be also be evaluated:

1. All-cause and cardiovascular mortality annually through 5 years
2. All stroke (disabling and non-disabling) annually through 5 years
3. Cardiovascular and heart failure hospitalizations at annually through 5 years
4. Heart failure events at annually through 5 years
5. New York Heart Association (NYHA) functional classification at 30 days, 6 months, and annually through 5 years
6. Change in New York Heart Association (NYHA) functional classification from baseline annually through 5 years
7. Kansas City Cardiomyopathy (KCCQ) annually through 5 years
8. Hemodynamic performance metrics by Doppler echocardiography
 - Mean aortic gradient annually through 5 years
 - Effective orifice area annually through 5 years
 - Degree of total, para, and transvalvular prosthetic regurgitation annually through 5 years
 - Incidence of moderate and severe patient-prosthesis mismatch (PPM) annually through 5 years
9. Prosthetic valve thrombosis 30 days, 6 months, and annually through 5 years
10. Prosthetic valve endocarditis at 30 days, 6 months, and annually through 5 years

11. Bioprosthetic valve dysfunction (BVD) at 30 days, 6 months, and annually through 5 years
12. Bioprosthetic valve failure (BVF) at 30 days, 6 months, and annually through 5 years
13. Valve-related dysfunction requiring repeat procedure annually through 5 years

Analyses of the additional outcome measures will be descriptive. The attempted implant set will be used for safety and quality of life outcomes. However, the outcomes involving echocardiographic variables will be analyzed for the implanted set. Continuous variables will be summarized as the number of subjects, mean, standard deviation, median, first and third quartiles, minimums, and maximums. Categorical variables will be summarized as counts and percentages. For each time-related event, Kaplan-Meier rates (cumulative incidence) and 95% two-sided confidence intervals will be calculated.

10.7 Sample Size Determination

As this is a descriptive study, the sample size of 75 subjects was not determined by statistical sample size methods. However, a sample size of 75 subjects is adequate to accomplish the study objectives and for an assessment of the procedural safety and efficacy of the study device in the study population.

10.8 Minimization of Bias

The study methods include the following measures to minimize potential sources of bias:

- An Eligibility Review Committee (ERC) will confirm each subject's eligibility for the study.
- An external, independent Clinical Events Committee (CEC) will adjudicate all deaths and safety-related endpoint events. Safety endpoint results will be based on CEC adjudications.
- Sites will follow a standardized protocol for acquisition of echocardiographic endpoint data.
- Echocardiographic endpoint results will be based on Echocardiography Core Lab assessments.
- A statistical analysis plan (SAP) will be developed prior to analyzing data. The plan will document all pre-specified analyses and analysis methods.

In summary, potential sources of bias that may be encountered in this study have been considered and minimized by careful study design.

11. Ethics and Regulatory Compliance

11.1 Statement(s) of Compliance

The Evolut™ EXPAND TAVR I Feasibility Study will be conducted in compliance with the current version of the Declaration of Helsinki, the International Conference on Harmonization (ICH) Good Clinical Practice (GCP) R2 guidelines, the study protocol, the Sponsor's standard operating procedures and/or guidelines, and in accordance with federal, national and local laws, regulations, standards, and requirements of the countries/geographies where the study is being conducted.

These include but are not limited to the following:

- In the United States, the study will be conducted under a US FDA Investigational Device Exemption (IDE) in compliance with 21 CFR Parts 11, 50, 54, 56 and 812, and ISO 14155:2020 (except for Adverse Event reporting after 6-month visit as noted in section 7.2)
- In the EMEA region the study will be conducted in compliance with ISO 14155:2020 (except for Adverse Event reporting after 6-month visit as noted in section 7.2). The laws and regulations of the countries in which the study is conducted, included data protection laws, must be followed.
- In Canada, SOR/98-282, Section 79-88 will be followed. The study will be conducted in compliance with ISO 14155:2020 (except for Adverse Event reporting after 6-month visit as noted in section 7.2)
- In Australia, New Zealand the study will be conducted in compliance with local regulations and ISO 14155:2020 (except for Adverse Event reporting after 6-month visit as noted in section 7.2)

In addition, the study will be conducted in compliance with 21 CFR Part 11 and 54 in all participating geographies.

